## 4.4 Sample size calculation

Sample size calculation is based on the estimated change in depressive symptoms form pre- to posttreatment. As we aim to include patients with all levels of depressive symptoms, we based our calculation on a previous study conducted at the Radboudumc Centre for Mindfulness (van Aalderen et al., 2012). In this study, levels of depression as assessed with the Inventory of depressive symptomatology – self-rated (IDS-SR) decreased in the MBCT+TAU group (n = 102) from 14.9 ( $\pm$  9.2) to 10.3 ( $\pm$  7.8) whereas the TAU group (n = 103) showed no change in depression levels (pretreatment: M = 16.2 ( $\pm$  9.4) and posttreatment: M = 16.2 ( $\pm$  9.8). This corresponded to an effect size of 0.5 for reduction of depressive symptoms in patients with recurrent (unipolar) depression (remitted n = 124, currently depressed n = 58). Based on a two-sided test with an alpha of 0.05 and a power of 80%, with an estimated effect size of 0.5, including a design factor of 1 – r2 (0.75), and taking account of a conservative estimate of 40% loss to follow-up, we intend to recruit N = 160 patients (80 per group).

We anticipate that about 25% of the population will have to be excluded due to (hypo)manic symptoms (when exceeding the maximum on the Young Mania Rating Scale) or other exclusion criteria. We further expect about 25% of the eligible patients to be interested in the study.

Approximately 690 BD patients are treated in ProPersona, with 518 (75%) meeting the inclusion criteria, of whom 130 (25%) would probably be interested to participate. The intended number of participants (n = 60) falls comfortably within this estimate. The number of BD patients treated in Dimence is about 900, with 675 (75%) meeting the inclusion criteria, of whom 169 (25%) would probably be interested to participate. Again, the intended number of participants (n = 50) falls well within this estimate. Approximately 650 BD patient are treated in Altrecht, with 100-150 new patients per year. About 487 (75%) of BD patients would be meeting the inclusion criteria, of whom 122 (25%) would probably be interested. The intended number of participants (n = 50) therefore seems feasible. Moreover, we will recruit patients through the patient association Vereniging voor Manisch Depressieven en Betrokkenen (VMDB) and the psychiatry department of the Canisius Wilhelmina

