## 5. TREATMENT OF SUBJECTS

## 5.1 Investigational treatment

## Mindfulness Based Cognitive Therapy (MBCT) + TAU

This intervention will consist of usual care, with MBCT in adjunct. MBCT is a manualised group skillstraining program (Segal, Williams, & Teasdale, 2012) designed as a relapse prevention programme for patients with recurrent depression. The training consists of eight weekly sessions of 2.5 hours, plus one day of silent practice. In addition, participants are instructed to practice 45 minutes a day. The program includes both formal and informal meditation exercises. Cognitive techniques that are part of the program include psychoeducation, monitoring and scheduling of activities, identification of negative automatic thoughts and devising a relapse prevention plan. The MBCT intervention offered in the current study will be based on the 8-week MBCT course developed by Segal et al. (2012), but will be adapted to address the needs of BD patients. A few examples of these adaptations are as follows: psychoeducation about manic symptoms in addition to psychoeduction about depression; introducing the 3-minute breathing space earlier in the programme and more often during sessions, especially when strong emotions are present; repeatedly bringing the focus to self-care; and making use of the mindful movement (yoga) exercises more frequently. All group sessions will be conducted at the respective mental health sites, with each group comprising 8 - 12 participants.

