# 8. STATISTICAL ANALYSIS

Multilevel analysis will be used to account for the cluster-randomized design and therefore the hierarchical structure of the data, with outcome variables at the pre- and postmeasurements at the lowest level, nested within individuals, nested within treatment groups (for the intervention condition), and nested within condition (MCBT + TAU vs TAU). Any baseline parameters that may be inadvertently unequally distributed between the conditions are included as covariates. Multilevel logistic regression will be performed for dichotomous outcomes and multilevel regression analysis for normally distributed continuous outcomes. The clinical outcome data will be analysed and reported according to the CONSORT guidelines, i.e. on intention-to-treat basis. Given the anticipated drop-out, we will also analyze and report on the per-protocol group, and discuss possible differences between the two analysis sets.

Additional analyses will be performed within subgroups with and without a current depressive episode. To account for possible differences between therapy groups, we will add a random group effect. Sensitivity analyses will be conducted with different scenarios of imputed data sets, in case of missing data, to examine the influence of missing data on the pattern of outcomes.

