#### Cost-effectiveness and cost-utility analysis

For these analyses we will use SPSS statistical software and Excel (for the Bootstraps). Respondents for whom at least 75% of the data per measurement instrument are available will be included in the analysis. Missing cost and outcome data will be imputed using multiple imputation (MI) methods and last-observation carried forward (LOCF), for intention to treat (ITT) analysis following Dutch guidelines (Zorginstituut Nederland 2016).

A baseline analysis will be performed to examine the comparability of groups at baseline for both costs and outcomes. If necessary methods will be applied to control for differences in baseline (Manca, Hawkins, & Sculpher, 2005). To investigate whether data are normally distributed a Kolmogorov-Smirnov test will be performed. Despite the usual skewness in the distribution of costs, the arithmetic means will be generally considered the most appropriate measures to describe cost data (Barber & Thompson, 2000; Ramsey et al., 2005). Therefore arithmetic means (and standard deviations) will be presented. In case of skewness of the cost data, non-parametric bootstrapping will be used to test for statistical differences in costs between the intervention and control group. Non-parametric bootstrapping is a method based on random sampling with replacement based on individual data of the participants (A. H. Briggs, Wonderling, & Mooney, 1997). The bootstrap replications will be used to calculate 95% confidence intervals around the costs (95% CI), based on the 2.5th and 97.5th percentiles. If cost data are distributed normally, t-tests will be used.

The Incremental cost-effectiveness ratio (ICER) will be determined on the basis of incremental costs and effects of MBCT compared to TAU. The cost-effectiveness ratio will be stated in terms of costs per outcome rate (IDS-C), the cost-utility ratio will focus on the cost per QALY gained.

The ICER will be calculated as follows. ICER = (Ci - Cc) / (Ei - Ec), where Ci is the total cost of the MCBT group, Cc is the total cost of the TAU group, Ei is the effect at 12 months follow-up for the MCBT group and Ec is the effect at 12 months follow-up for the TAU group.

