## Sensitivity analysis

Stochastic uncertainty of the ICER will be handled using 2,500 non-parametric bootstraps and by plotting the simulated ICERs on the ICER plane. Bootstrap simulations will be conducted in order to quantify the uncertainty around the ICER, yielding information about the joint distribution of cost and effect differences. The bootstrapped cost-effectiveness ratios will be subsequently plotted in a cost-effectiveness plane, in which the vertical line reflects the difference in costs and the horizontal line reflects the difference in effectiveness. The choice of treatment depends on the maximum amount of money that society is prepared to pay for a gain in effectiveness, which is called the willingness-to-pay (WTP) ceiling ratio. For decision-making purposes, the ICER acceptability curve will be plotted for various WTP) ceilings for making judgments whether discontinuation offers good value for money relative to routine medical care. Deterministic one-way sensitivity analyses directed at uncertainty in the main effects and main cost drivers will be performed to assess the robustness of our findings. Additionally, a multi-way sensitivity (scenario-) analyses will recalculated in order to assess whether the assumptions have influenced the incremental cost-effectiveness ratio (ICER), for example by varying cost-prices and volumes between minimum and maximum (A. H. Briggs et al., 1997).

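### The economic analysis leaves out the therapy-group level that Section 8 puts into the clinical models, so its intervals are too narrow if costs or effects correlate within MBCT groups

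*Protocol*

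**What the plan says.** Section 8 describes the data as hierarchical, with treatment groups as a level in the intervention arm, and adds: "To account for possible differences between therapy groups, we will add a random group effect". Section 5.1 has MBCT delivered in groups, "with each group comprising 8 - 12 participants". TAU has no corresponding grouping.

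The cost-effectiveness and cost-utility part of Section 8.2 names separate methods and software, with the bootstraps assigned to Excel. For skewed costs the arms are compared by a non-parametric bootstrap, explained as "random sampling with replacement based on individual data of the participants". The text continues: "The bootstrap replications will be used to calculate 95% confidence intervals around the costs (95% CI), based on the 2.5th and 97.5th percentiles". The other route is: "If cost data are distributed normally, t-tests will be used".

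The sensitivity analysis part then states: "Stochastic uncertainty of the ICER will be handled using 2,500 non-parametric bootstraps". These replicates feed the cost-effectiveness plane, and an acceptability curve is to be drawn for decision-making. Neither part mentions a therapy group, a cluster or two-stage bootstrap, or a multilevel cost model.

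**The concern.** An individual-level bootstrap or an ordinary t-test treats the MBCT patients as independent. Section 8 allows that they may not be, because those who share a group share a teacher and each other. With positive correlation inside groups, the MBCT mean varies more than individual resampling can show.

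The protocol would then report IDS-C with a therapy-group adjustment in the clinical analysis and without one in the cost-effectiveness ratio, which also uses IDS-C as its effect. Cost-effectiveness is a stated secondary objective. What is at stake is how certain the trial appears to be about value for money.

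**Working it through.** **The protocol's own figure.** It states no width for the economic intervals, so the only figure to reproduce is the sample size in Section 4.4: "Based on a two-sided test with an alpha of 0.05 and a power of 80%, with an estimated effect size of 0.5". The standard two-sample formula gives 2 × (1.96 + 0.84)² / 0.5² = 62.8, so 63 per arm. Multiplying by the design factor 0.75 gives 47.25, so 48. Dividing by 1 − 0.40 gives 80 per arm, 160 in total, as stated. The factor 0.75 is 1 − r², a gain from baseline adjustment. It is not an allowance for clustering.

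**Inputs.** Group size m = 8 to 12 (Section 5.1), grouping in the MBCT arm only (Section 8), equal arms and 40% loss (Section 4.4). The ICC is not given. I assume 0 to 0.10 and equal total variance in the two arms.

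**Formula.** With n analysed per arm and variance σ², individual resampling reflects a variance of 2σ²/n for the difference. With groups in one arm the variance is (σ²/n)[1 + (m − 1)ICC] + σ²/n. The ratio of true to individual-level standard error is therefore √{[2 + (m − 1)ICC]/2}, and the coverage of a nominal 95% interval is 2Φ(1.96/ratio) − 1.

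Example with m = 10 and ICC = 0.05: √(2.45/2) = 1.107, coverage 92.3%.

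If the 40% loss falls evenly, 8 × 0.6 = 4.8 and 12 × 0.6 = 7.2 members per group remain. With m = 6 and ICC = 0.05: √(2.25/2) = 1.061, coverage 93.5%.

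| ICC | SE ratio, m = 8 to 12 | Coverage | SE ratio, m = 4.8 to 7.2 | Coverage |
|---|---|---|---|---|
| 0 | 1.000 | 95.0% | 1.000 | 95.0% |
| 0.01 | 1.017 to 1.027 | 94.6% to 94.4% | 1.009 to 1.015 | 94.8% to 94.6% |
| 0.02 | 1.034 to 1.054 | 94.2% to 93.7% | 1.019 to 1.031 | 94.6% to 94.3% |
| 0.05 | 1.084 to 1.129 | 92.9% to 91.7% | 1.046 to 1.075 | 93.9% to 93.2% |
| 0.10 | 1.162 to 1.245 | 90.8% to 88.5% | 1.091 to 1.145 | 92.8% to 91.3% |

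**Simulation check.** Skewed costs, 80 per arm, 8 MBCT groups of 10, 1,500 trials with 1,000 resamples each, percentile intervals:

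| ICC | Coverage, individual bootstrap | Coverage, whole-group bootstrap | Mean width, individual bootstrap | True 95% spread |
|---|---|---|---|---|
| 0 | 93.5% | 92.1% | 0.61 SD | 0.65 SD |
| 0.01 | 94.2% | 93.2% | 0.61 SD | 0.63 SD |
| 0.05 | 91.1% | 91.9% | 0.61 SD | 0.69 SD |
| 0.10 | 88.6% | 91.4% | 0.61 SD | 0.75 SD |

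The individual bootstrap keeps the same width while the true spread grows. Resampling whole groups helps at higher ICC but still under-covers, because 80 patients form only about 7 groups (80/12) to 10 groups (80/8).

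**The case against.** The quoted sentence reads partly as a textbook definition of bootstrapping, it stands in the cost comparison, and the sensitivity analysis part does not restate a resampling unit for the ICER. A reader might infer that the protocol expressly orders individual resampling for the ICER. It does not. That step is an extension, although no other unit is named anywhere and nothing in the later part changes it. The concern still stands for costs: the definition sits between the statement that bootstrapping will test the cost difference and the statement that its percentiles give the interval, and the t-test route has no group level either. This is a stated method, not detail left to a later plan.

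A reader might also infer that the intervals are too narrow whatever the data show. The documents do not support that. They give no ICC, call differences between therapy groups only possible, and say nothing about correlation in costs. At ICC 0.01 with full groups the understatement is 2% to 3%.

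The upper figures, a factor of 1.25 and coverage of 88%, need an ICC of 0.10 and complete data from groups of 12. The planned 40% loss makes that unlikely, although the planned imputation means the reduced group sizes are only a guide. Some similarity within a group is also shared with TAU patients at the same site, and randomisation is stratified by site, so only the excess group correlation matters. An unstratified bootstrap also ignores any precision gained from stratification, which works the other way. Neither effect can be sized from the protocol.

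In the simulation the individual bootstrap covered 93.5% even at ICC 0, so not all of the simulated shortfall comes from clustering.

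Finally, the ICER uses the 12-month effect and the primary endpoint is at 3 months. The mismatch is therefore between two analyses of the same scale, not of the same number.

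**Conclusion.** The point holds in conditional form. The economic analysis omits a level that Section 8 includes, and for any positive excess correlation within therapy groups its uncertainty is understated. Under an assumed ICC of 0.02 to 0.10, equal variances and equal arms, the understatement of the standard error runs from about 2% in the mildest case (small remaining groups, ICC 0.02) to about 25% in the most severe (full groups of 12, ICC 0.10). Because only one arm is grouped, the extra variance of the difference is half what it would be if both arms were grouped. The effect is confined to the cost intervals, the ICER cloud and the acceptability curve. A reader might infer that the main result is also at risk, but the primary IDS-C analysis has its own multilevel model and the ICER point estimate does not depend on how resampling is done. It is worth correcting because the change only carries the protocol's own adjustment into its secondary economic objective.

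**What to change.** State in Section 8.2 that the economic uncertainty analysis respects therapy groups in the MBCT arm, by one of two routes:

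- a multilevel bivariate model for cost and effect, with a therapy-group random effect in the MBCT arm only; or
- a two-stage bootstrap, stratified by arm: in MBCT resample groups and then patients within groups, in TAU resample patients. Each patient's cost and effect stay paired, and a small-sample (shrinkage) correction is applied because there are only about 7 to 10 groups.

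Replace the plain t-test in the same way, and say that the 2,500 ICER replicates follow the same scheme.

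The cost is some more analysis work in a statistics package instead of Excel, and slightly wider intervals. No extra patients or data are needed, provided each MBCT patient's group is recorded, which the random effect in Section 8 already requires. Coverage will remain imperfect with so few groups: whole-group resampling alone reached only about 91% to 93% in the simulation, and the corrected two-stage version was not simulated here.

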## Sensitivity analysis

Stochastic uncertainty of the ICER will be handled using 2,500 non-parametric bootstraps and by plotting the simulated ICERs on the ICER plane. Bootstrap simulations will be conducted in order to quantify the uncertainty around the ICER, yielding information about the joint distribution of cost and effect differences. The bootstrapped cost-effectiveness ratios will be subsequently plotted in a cost-effectiveness plane, in which the vertical line reflects the difference in costs and the horizontal line reflects the difference in effectiveness. The choice of treatment depends on the maximum amount of money that society is prepared to pay for a gain in effectiveness, which is called the willingness-to-pay (WTP) ceiling ratio. For decision-making purposes, the ICER acceptability curve will be plotted for various WTP) ceilings for making judgments whether discontinuation offers good value for money relative to routine medical care. Deterministic one-way sensitivity analyses directed at uncertainty in the main effects and main cost drivers will be performed to assess the robustness of our findings. Additionally, a multi-way sensitivity (scenario-) analyses will recalculated in order to assess whether the assumptions have influenced the incremental cost-effectiveness ratio (ICER), for example by varying cost-prices and volumes between minimum and maximum (A. H. Briggs et al., 1997).

## Budget-impact analysis

The budget impact analysis (BIA) will be conducted as outlined by the ISPOR Task Group (i.e. Mauskopf et al., 2007; Sullivan et al., 2014) to assess how health care budgets change when MCBT is offered over a range of implementation levels. The BIA will be conducted from various perspectives: (1) the societal perspective, i.e. including productivity losses; (2) the perspective of the public purse (in Dutch: netto Budgettair Kader Zorg); and (3) the perspective of the health care insurer. In each perspective the following scenarios will be assessed: a scenario in which the intervention is offered to 40%, 60% and 80% of the target group and an extreme scenario in which 100% of the target group will be receiving the MCBT intervention. These scenarios will be compared with a base-case scenario

where 0% of the target group is offered MCBT (reflecting treatment as usual (TAU). The BIA will be based on a health-economic simulation excel model, based on modelling techniques outlined in Briggs, Claxton, & Sculpher (2006) and following ISPOR modeling guidelines (Caro, Briggs, Siebert, & Kuntz, 2012). The BIA will be conducted according Dutch guidelines (Zorginstituut Nederland, 2016), taking into account the complexity and dynamics of clinical practice and specific characteristics of the Dutch health care system. Cost data will be extracted from the trial and are based on the Dutch manual of costing (Tan, Bouwmans-Frijters, & Hakkaart-van Roijen, 2012). Costs will be modelled out over the short term (12 months) and longer-term (36 months) as required by the Dutch guideline for health-economic evaluation (Zorginstituut Nederland, 2016). Long-term costs will be discounted according to the Dutch guidelines. The impact of MBCT on budgets is furthermore depending on (changes in) the prevalence of BD. Sensitivity analyses on the main input parameters will be conducted to assess the robustness of the outcomes.

## 8.3 Other study parameters

The potential effects of CTEs on MBCT treatment effect will be assessed by moderation analysis. Furthermore, we will assess whether MBCT induces change in the acquired cognitive-affective bias measures. In addition, mediation analysis will be used to study the effect of MBCT on cognitive control measures (cognitive-affective bias, rumination) in the MBCT + TAU versus the TAU group. Mediation and moderation analyses will be carried out using the PROCESS tool (Hayes, 2012). With PROCESS, estimates of mediation/moderation effects were computed using bootstrapping methods.

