## 2. OBJECTIVES

Primary Objective:

• Is MBCT as an adjunctive treatment to TAU more effective in reducing depressive symptoms in patients with bipolar disorder, compared to TAU alone?

Secondary Objective(s):

- Is MBCT more effective than TAU in reducing levels of (hypo)manic and anxiety symptoms, the risk of relapse in depression or (hypo)mania, and ruminative brooding?
- Is MBCT equally effective in patients with < 12 mood episodes compared to patients with =/> 12 episodes?
- Is MBCT more effective than TAU in improving mindfulness, self-compassion, functioning, and mental health/well-being?
- From the viewpoint of the society, is adding MBCT to TAU preferable in terms of societal costs and QALYs, compared to TAU alone?

Our hypothesis is that participants allocated to MBCT will have fewer depressive, (hypo)manic, and anxiety symptoms and experience fewer (hypo)manic or depressive episodes than those allocated to TAU over the 15 months study period. In addition, we hypothesize that MBCT will be associated with improvement in several areas of functioning and well-being. Furthermore, we expect that positive outcomes will be (partially) mediated by a reduction of ruminative thinking, and improvement of mindfulness and self-compassion skills.

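### The mediation analysis in section 8.3 does not test the mediation hypothesis of section 2, and it leaves out the therapy-group effect that section 8 adds

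*Protocol*

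**What the plan says.** **Hypothesis.** Section 2 expects positive outcomes to be at least partly "mediated by a reduction of ruminative thinking, and improvement of mindfulness and self-compassion skills". The Summary names mindfulness and self-compassion as possible working mechanisms. The end of section 1 lists both again, with rumination and cognitive-affective bias.

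**Analysis.** Section 8.3 states that "mediation analysis will be used to study the effect of MBCT on cognitive control measures (cognitive-affective bias, rumination" being the two examples given in brackets. It continues: "Mediation and moderation analyses will be carried out using the PROCESS tool", with bootstrapped estimates. It mentions no therapy-group term. Section 8.2 analyses the mindfulness (CHIME) and self-compassion (SCS-SF) totals as secondary outcomes; no part of section 8 gives them a mediating role.

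**Clustering.** The general text of section 8 nests patients within treatment groups in the intervention condition and says: "To account for possible differences between therapy groups, we will add a random group effect". This is not limited to one endpoint. Section 5.1 sets the group size at 8 to 12.

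**Data.** Table 1 schedules the brooding scale, SCS-SF, CHIME and RPA-NL at T0, during MBCT and at T1 to T5. IDS-C is taken at T0 and T1 to T5. The cognitive tasks are marked at T0 and T1 only.

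**The concern.** There are two separate problems.

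1. **Mediators.** The mechanism hypothesis is stated in section 2, and patients are asked for mid-treatment measurements of exactly these processes. Yet the planned mediation analysis leaves out two of the three processes and does not say which clinical outcome is mediated. If mediators, outcome and time points are settled only after the data are seen, the mechanism results are open to selective reporting.

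2. **Clustering.** Patients taught in the same MBCT group may resemble one another on the mediators, which is why section 8 adds a group effect. A mediation analysis without that effect treats them as independent and overstates the precision of the path from condition to mediator. The protocol itself shows the change of tool and the absence of a group term. That PROCESS fits single-level regressions is general methods knowledge and is not stated in the protocol.

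**Working it through.** **Step 1. Hypothesis against analysis.**

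| Element | Section 2 | Mediation in section 8.3 |
|---|---|---|
| Rumination | mediator | named |
| Mindfulness (CHIME) | mediator | not named; an outcome in 8.2 |
| Self-compassion (SCS-SF) | mediator | not named; an outcome in 8.2 |
| Cognitive-affective bias | not in the hypothesis (a mechanism in section 1) | named |
| What is mediated | positive outcomes | nothing named |

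One of the three hypothesised mediators appears in 8.3 and two do not.

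**Step 2. The plan's own sample size.** Inputs from section 4.4: two-sided test at 5%, 80% power, standardised effect 0.5, a multiplier of 0.75 for the baseline correlation, and 40% loss.

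- Per arm: 2 × (1.960 + 0.842)² / 0.5² = 62.8
- Times 0.75: 47.1, rounded up to 48
- Divided by 0.60: 80 per arm, 160 in total

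This reproduces the stated figure: "we intend to recruit N = 160 patients (80 per group". The 0.75 reflects a baseline correlation of 0.5 and contains no therapy-group term. The point disputes no figure here.

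**Step 3. Effect of ignoring therapy groups on the condition-to-mediator path.** Only the MBCT arm is clustered and the arms are equal in size. With m analysed patients per group:

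- Design effect in the MBCT arm: DE = 1 + (m − 1) × ICC
- Standard error factor for the arm contrast: √((DE + 1)/2)
- True type I error of a nominal 5% test: 2 × (1 − Φ(1.96 / factor))

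The protocol gives no ICC, so 0.02 to 0.10 is assumed. Group size is 8 to 12, or 8 × 0.6 = 4.8 to 12 × 0.6 = 7.2 (about 5 to 7) if the planned 40% loss falls evenly on the groups.

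| m | ICC | DE | SE factor | Type I error |
|---|---|---|---|---|
| 8 | 0.02 | 1.14 | 1.03 | 0.058 |
| 10 | 0.05 | 1.45 | 1.11 | 0.077 |
| 12 | 0.10 | 2.10 | 1.24 | 0.115 |
| 4.8 | 0.02 | 1.076 | 1.02 | 0.054 |
| 6 | 0.05 | 1.25 | 1.06 | 0.065 |
| 7.2 | 0.10 | 1.62 | 1.14 | 0.087 |

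**Step 4. Check by simulation.** Ordinary regression was applied to 80 patients per arm with clustering in the MBCT arm only (6,000 replicates). For groups of 10 the type I error was 0.078 at ICC 0.05 and 0.103 at ICC 0.10, against 0.077 and 0.104 by formula. For groups of 8 it was 0.070 and 0.097, against 0.071 and 0.092.

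**Step 5. Moderation by childhood trauma.** The same simulations tested a condition-by-moderator interaction with an individual-level moderator. With a random group intercept the type I error was 0.046 to 0.054, so there is essentially no inflation. It reached about 0.074 only when the moderator's slope was also made to vary between groups (assumed slope variance 0.05).

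**The case against.** **Detail for the SAP.** Section 8.3 concerns exploratory analyses, and the outcome and time points of a mediation model are commonly left to a statistical analysis plan, which is not at hand. Mindfulness and self-compassion are measured and analysed as outcomes. This stands as far as time points go. It does not answer the mismatch: the protocol gives a list of mediators, and that list conflicts with its own hypothesis.

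**Mediator and outcome swapped.** A reader might infer that 8.3 treats cognitive bias and rumination as outcomes rather than mediators. The preceding sentence in 8.3 already covers change in the bias measures, so the natural reading is that they are mediators and the mediated outcome was left unnamed.

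**Trauma moderation.** A reader might also infer that the trauma-moderation intervals would be too narrow. Step 5 does not support this under the random group effect that section 8 describes.

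**Lost patients.** A third tempting inference is that the analysis would drop 40% of patients, leaving 160 × 0.6 = 96. Section 8.3 says nothing about complete cases. Section 4.4 calls the 40% conservative, section 8 plans sensitivity analyses with imputed data, and section 6.6 has dropouts contacted for the remaining questionnaires.

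**Size.** The 12% figure needs full groups and an ICC of 0.10. With losses near the planned rate the lower range applies. The formula covers the condition-to-mediator path only; an indirect effect is a product of two paths, and its error is not quantified here.

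**Conclusion.** The point holds, as a desirable correction to an exploratory analysis. Section 8.3 as written would not test the mediation hypothesis of section 2: two of the three mediators are missing and no mediated outcome is named. This can be read from the protocol alone.

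The clustering part also holds, modestly, for the condition-to-mediator path. For an assumed ICC of 0.02 to 0.10 its standard error is understated by a factor of 1.03 to about 1.25 with full groups (type I error about 6 to 12%), or 1.02 to 1.14 with 5 to 7 analysed per group (about 5 to 9%). This rests on the assumed ICC and on PROCESS being used without a group term. It does not extend to the trauma moderation or to a loss of 40% of patients, and the primary IDS-C comparison and N = 160 are unaffected.

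**What to change.** In section 8.3:

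- Name rumination, mindfulness (CHIME) and self-compassion (SCS-SF) as mediators of IDS-C, and keep cognitive-affective bias. State which instrument represents rumination.
- Measure the mediator before the outcome: mid-treatment scores for IDS-C at T1 where they are collected, or T1 scores for later IDS-C. As Table 1 stands, cognitive-affective bias allows only the second option.
- Adjust for the baseline mediator and baseline IDS-C.
- Fit the mediation paths with the random therapy-group effect of section 8. This is preferable to bootstrapping whole therapy groups: 80 patients in groups of 8 to 12 give only about 7 to 10 groups to resample (80/12 = 6.7; 80/8 = 10).
- Optionally, test trauma moderation as an interaction in the main multilevel model, for consistency with section 8.

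Cost: a change of wording, somewhat more analysis work and slightly wider intervals. No new patients, visits or measurements are needed.
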